8. BIOSPECIMEN STUDIES AND PROCEDURES

Please refer to the Correlative Laboratory Manual (CLM) for additional details on studies outlined below.

8.1 Tissue

8.1.1 Archival Tissue

Archival tissue is required if available. Archival tissue should be identified at screening, requested after registration and shipped by C2D1. If archival tissue is not available, subjects may still be eligible. This tissue will be used to analyze EZH2 expression.

8.1.2 Fresh Biopsy Tissue

For 15 patients with easily accessible disease, biopsies are required Cycle 1 Day 1 (regardless of archival tissue availability) and Cycle 2 Day 5 to assess methylation changes, EZH2 expression, and platinum-induced DNA adducts. A biopsy at progression is optional for the same 15 patients and similar analysis will be performed.

8.2 Peripheral Blood Samples

8.2.1 Somatic Baseline

Whole blood will be collected for somatic baseline prior to treatment C1D1. This sample is required.

8.2.2 Circulating Tumor Cells (CTCs)

Whole blood will be collected for CTCs prior to treatment C1D1. This sample is required and will be used to determine circulating tumor cell (CTC) burden prior to initiating treatment.

8.2.3 Peripheral Blood Mononuclear cells

Whole blood will be collected prior to treatment on C1D1, C2D5 and at progression for isolation of peripheral blood mononuclear cells. Changes in LINE1 methylation levels in PBMCs will be assessed. In addition, platinum induced DNA lesions will be quantified. DNA will be extracted and ICP-MS performed to determine global DNA lesions.

8.3 Samples for future unspecified cancer related

Subject consent will be obtained to collect additional samples for future unspecified cancer related research. Hoosier Cancer Research Network will manage the banked samples. Samples will be banked indefinitely in the Hoosier Cancer Research Network Biorepository until they are used up. Collection of samples is optional.

This includes:

- Whole blood: Whole blood will be collected prior to treatment on Cycle 1 Day 1.
- Pre- and Post-treatment plasma: Whole blood for plasma will be collected prior to treatment on Cycle 1 Day 1 and at the 30-day Safety Follow-up visit.
- Pre- and Post-treatment serum: Whole blood for serum will be collected prior to treatment on Cycle 1 Day 1 and at the 30-day Safety Follow-up visit.

Version Date: 18MAR2020 Confidential Page 22 of 41

Please refer to the Correlative Laboratory Manual (CLM) for all sample collection, processing, labeling, and shipping instructions.

8.4 Storage of Biospecimens

Any specimens remaining (leftover) once protocol described biospecimen-based studies are complete will be stored for future unspecified cancer related research. Permission to store these samples will be obtained during informed consent.

8.5 Confidentiality of Biospecimens

Samples that are collected will be identified by a subject's sequence ID assigned at the time of registration to the trial. Any material issued to collaborating researchers will be anonymized and only identified by the subject's study number.

9. CRITERIA FOR DISEASE EVALUATION

9.1 Measurable Disease

Measurable disease is defined as the presence of at least one measurable lesion. Measurable lesions are defined as those that can be accurately measured in at least one dimension (longest diameter to be recorded) as \geq 20 mm by chest x-ray, as \geq 10 mm with CT scan, or \geq 10 mm with calipers by clinical exam. All tumor measurements must be recorded in millimeters (or decimal fractions of centimeters).

9.1.1 Malignant Lymph Nodes

To be considered pathologically enlarged and measurable, a lymph node must be ≥ 15 mm in short axis when assessed by CT scan (CT scan slice thickness recommended to be no greater than 5 mm). At baseline and in follow-up, only the short axis will be measured and followed.

9.2 Non-measurable Lesions

All other lesions (or sites of disease), including small lesions (longest diameter <10 mm or pathological lymph nodes with ≥ 10 to <15 mm short axis), are considered non-measurable disease. Bone lesions, leptomeningeal disease, ascites, pleural/pericardial effusions, lymphangitis cutis/pulmonitis, inflammatory breast disease, and abdominal masses (not followed by CT or MRI), are considered as non-measurable.

NOTE: Cystic lesions that meet the criteria for radiographically defined simple cysts should not be considered as malignant lesions (neither measurable nor non-measurable) since they are, by definition, simple cysts. 'Cystic lesions' thought to represent cystic metastases can be considered as measurable lesions, if they meet the definition of measurability described above. However, if non-cystic lesions are present in the same subject, these are preferred for selection as target lesions.

9.3 Target Lesions

All measurable lesions up to a maximum of 2 lesions per organ and 5 lesions in total, representative of all involved organs, should be identified as target lesions and recorded and measured at baseline. Target lesions should be selected on the basis of their size (lesions with the longest diameter), be representative of all involved organs, but in addition should be those that

Version Date: 18MAR2020 Confidential Page 23 of 41

lend themselves to reproducible repeated measurements. It may be the case that, on occasion, the largest lesion does not lend itself to reproducible measurement in which circumstance the next largest lesion which can be measured reproducibly should be selected. A sum of the diameters (longest for non-nodal lesions, short axis for nodal lesions) for all target lesions will be calculated and reported as the baseline sum diameters. If lymph nodes are to be included in the sum, then only the short axis is added into the sum. The baseline sum diameters will be used as reference to further characterize any objective tumor regression in the measurable dimension of the disease.

9.4 Non-target Lesions

All other lesions (or sites of disease) including any measurable lesions over and above the 5 target lesions should be identified as non-target lesions and should also be recorded at baseline. Measurements of these lesions are not required, but the presence, absence, or in rare cases unequivocal progression of each should be noted throughout follow-up.

9.5 Evaluation of Target Lesions

NOTE: In addition to the information below, also see section 4.3.2 in the international criteria proposed by the Response Evaluation Criteria in Solid Tumors (RECIST) Committee, version 1.1 (Eur J Cancer 45;2009:228-247) for special notes on the assessment of target lesions.

Complete Response (CR)	Disappearance of all target lesions. Any pathological lymph nodes
	(whether target or non-target) must have reduction in short axis to
	<10 mm.
Partial Response (PR)	At least a 30% decrease in the sum of the diameters of target
	lesions, taking as reference the baseline sum diameters
Progressive Disease (PD)	At least a 20% increase in the sum of the diameters of target
	lesions, taking as reference the smallest sum on study (this includes
	the baseline sum if that is the smallest on study). In addition to the
	relative increase of 20%, the sum must also demonstrate an
	absolute increase of at least 5 mm. (Note: the appearance of one or
	more new lesions is also considered progressions).
Stable Disease (SD)	Neither sufficient shrinkage to qualify for PR nor sufficient
	increase to qualify for PD, taking as reference the smallest sum
	diameters while on study

9.6 Evaluation of Non-Target Lesions

Complete	Disappearance of all non-target lesions and normalization of tumor marker
Response (CR)	level. All lymph nodes must be non-pathological in size (<10 mm short axis)
	NOTE : If tumor markers are initially above the upper normal limit, they must
	normalize for a subject to be considered in complete clinical response.
Non-CR/ Non-	Persistence of one or more non-target lesion(s) and/or maintenance of tumor
PD	marker level above the normal limits
Progressive	Appearance of one or more new lesions and/or unequivocal progression of
Disease (PD)	existing non-target lesions. Unequivocal progression should not normally
	trump target lesion status. It must be representative of overall disease status
	change, not a single lesion increase.

Version Date: 18MAR2020 Confidential Page 24 of 41

Although a clear progression of "non-target" lesions only is exceptional, the opinion of the site investigator should prevail in such circumstances, and the progression status should be confirmed at a later time by the sponsor investigator.

9.7 Evaluation of Best Overall Response

Target Lesions	Non-Target Lesions	New Lesions	Overall Response
CR	CR	No	CR
CR	Non-CR/ Non-PD	No	PR
CR	Not evaluated	No	PR
PR	Non-PD/ or not all evaluated	No	PR
SD	Non-PD or not all evaluated	No	SD
Not all evaluated	Non-PD	No	Non-evaluable
PD	Any	Yes or No	PD
Any	PD*	Yes or No	PD
Any	Any	Yes	PD

^{*}In exceptional circumstances, unequivocal progression in non-target lesions may be accepted as disease progression.

Subjects with a global deterioration of health status requiring discontinuation of treatment without objective evidence of disease progression at that time should be classified as having "symptomatic deterioration." Every effort should be made to document the objective progression even after discontinuation of treatment.

In some circumstances, it may be difficult to distinguish residual disease from normal tissue. When the evaluation of complete response depends on this determination, it is recommended that the residual lesion be investigated (fine needle aspirate/biopsy) to confirm the complete response status.

9.8 Definitions for Response Evaluation – RECIST 1.1

9.8.1 Objective Response Rate

The objective response rate is the proportion of all subjects with confirmed PR or CR according to RECIST 1.1, from the start of treatment until disease progression/recurrence (taking as reference for progressive disease the smallest measurements recorded since the start of treatment).

9.8.2 Disease Control Rate

The disease control rate is the proportion of all subjects with stable disease (SD) for 8 weeks, or partial response (PR), or complete response (CR) according to RECIST 1.1, from the start of treatment until disease progression/recurrence (taking as reference for progressive disease the smallest measurements recorded since the start of treatment).

Version Date: 18MAR2020 Confidential Page 25 of 41

9.8.3 Progression Free Survival

A measurement from Day 1 of treatment until the criteria for disease progression is met as defined by RECIST 1.1 or death, whichever occurs first. Subjects who have not progressed will be right-censored at the date of the last disease evaluation.

10 DRUG INFORMATION

10.1 Guadecitabine; SGI-110

Guadecitabine is a potent inhibitor of DNA methylation that has been shown to induce a dose-dependent decrease of global DNA and gene-specific methylation in many different human cancer cell lines.

10.1.1 Supplier/How Supplied

Astex Pharmaceuticals will supply Guadecitabine at no charge to subjects participating in this clinical trial.

The investigator shall take responsibility for and shall take all steps to maintain appropriate records and ensure appropriate supply, storage, handling, distribution, and usage of investigational product in accordance with the protocol and any applicable laws and regulations.

10.1.2 Preparation

Guadecitabine is available as a two-vial system, referred to as (1) Guadecitabine for Injection, 100mg and (2) Guadecitabine Diluent for Reconstitution, 3mL or 1.2mL:

- Guadecitabine for Injection, 100mg contains guadecitabine, 100mg as a dry lyophilized powder
- Guadecitabine Diluent for Reconstitution, 3mL contains 3mL of a non-aqueous diluent for constitution. 1.2mL contains 1.2mL of a non-aqueous diluent.

The diluent is comprised of 3 commonly used excipients, propylene glycol, glycerin and ethanol, which are generally recognized as safe. All 3 excipients are pharmaceutically acceptable solvents previously in drug productions approved for SC administration. Guadecitabine solution is reconstituted at a maximum concentration of 100mg/mL for SC administration.

Both product and diluent are contained in clear glass vials stoppered with a latex-free rubber stopper and capped with an aluminum flip-off seal.

10.1.3 Storage and Stability

Guadecitabine for Injection, 100mg vial is stored at 2°C to 8 °C in the original packaging until use. Guadecitabine Diluent for Reconstitution, 3mL is stored at 2°C to 30 °C, and 1.2 mL is stored at 2°C to 8°C, both in an upright position until use. Both vials are preservative free and for single use only.

10.1.4 Handling and Disposal

Occupational Safety and Health Administration (OSHA) Guidelines for handling cytotoxic drugs outlined in the American Journal of Hospital Pharmacy should be followed. As with other potentially toxic anti-cancer agents, care should be exercised in the handling and preparation of guadecitabine. The use of gloves and protective garments is recommended. Preparation should occur in a vertical laminar flow biological hood using proper aseptic technique. Reconstituted drug product is intended for SC administration at a recommended concentration of 100 mg/mL.

Version Date: 18MAR2020 Confidential Page 27 of 41

10.1.5 Dispensing

Guadecitabine must be dispensed only from official study sites and to eligible subjects under the supervision of the site investigator. Guadecitabine be stored in a secure area according to local regulations. It is the responsibility of the site investigator to ensure that study drug is only dispensed to subjects.

10.1.6 Adverse Events

Please refer to the current version of the Investigator's Brochure (IB) for additional information regarding this drug.

10.2 Carboplatin

Please see product package insert for complete details regarding Carboplatin.

10.2.1 Availability

Carboplatin is commercially available.

10.2.2 Chemical Name

Carboplatin (carboplatin for injection or platinum diamine [1,1-cyclobutane- decarbozxylate (2—0,0')-,(SP-4-2)]) is a platinum compound used as a chemotherapeutic agent. It will be supplied commercially.

10.2.3 Formulation

Carboplatin is available as a sterile lyophilized powder in single-dose vials containing 50 mg, 150 mg, or 450 mg of carboplatin. Each vial contains equal parts by weight of carboplatin and mannitol. Commercial supplies of carboplatin will be used in this study.

10.2.4 Preparation

Immediately before use, the contents of a carboplatin vial must be reconstituted with either sterile water for injection, USP, 5% dextrose in water, or 0.9% sodium chloride injection, USP. The following shows the proper diluent volumes to be used to obtain a carboplatin concentration of 10 mg/mL. Carboplatin solution can be further diluted to concentrations as low as 0.5 mg/mL with D5W or 0.9% normal saline. Carboplatin reacts with aluminum to form a precipitate and cause a loss of potency. Therefore, needles or intravenous sets containing aluminum parts that may come in contact with the drug must not be used for the preparation or administration of carboplatin.

10.2.5 Storage and Stability

Intact vials of carboplatin are stable for the period indicated on the package when stored at room temperature (15-30°C or 59-86°F) and protected from light. When prepared as described above, carboplatin solutions are stable for 8 hours at room temperature if protected from light. The solution should be discarded after 8 hours since no antibacterial preservative is contained in the formulation.

10.2.6 Adverse Events Associated with Carboplatin

Incidence rates of adverse events associated with carboplatin are provided in the product package insert.

Version Date: 18MAR2020 Confidential Page 28 of 41

11 ADVERSE EVENTS

The descriptions and grading scales found in the NCI CTCAE v5.0 will be utilized for AE assessment. A copy of the CTCAE v5.0 can be downloaded from the CTEP website at http://ctep.cancer.gov. All forms for AE/SAE recording and reporting can be found in the EDC system (Documents and Information Tab).

11.1 Definitions

11.1.1 Adverse Event

An AE is any untoward medical occurrence whether or not considered related to the study drug that appears to change in intensity during the course of the study. The following are examples of AEs:

- Unintended or unfavorable sign or symptom
- A disease temporally associated with participation in the protocol
- An intercurrent illness or injury that impairs the well-being of the subject

Abnormal laboratory values or diagnostic test results constitute AEs only if they induce clinical signs or symptoms or require treatment or further diagnostic tests

Hospitalization for elective surgery or routine clinical procedures that are not the result of an AE (e.g., surgical insertion of central line) should not be recorded as an AE.

Disease progression should not be recorded as an AE, unless it is attributable to the study regimen by the site investigator.

11.1.2 Serious Adverse Event (SAE)

A SAE is an adverse event that:

- Results in death. **NOTE:** Death due to disease progression should not be reported as a SAE, unless it is attributable by the site investigator to the study drug(s)
- Is life-threatening (defined as an event in which the subject was at risk of death at the time of the event; it does not refer to an event which hypothetically might have caused death if it were more severe)
- Requires inpatient hospitalization for >24 hours or prolongation of existing hospitalization. **NOTE:** Hospitalization for anticipated or protocol specified procedures such as administration of chemotherapy, central line insertion, metastasis interventional therapy, resection of primary tumor, or elective surgery, will not be considered serious adverse events.
- Results in persistent or significant disability/incapacity
- Is a congenital anomaly or birth defect
- Is an important medical event (defined as a medical event(s) that may not be immediately life-threatening or result in death or hospitalization but, based upon appropriate medical and scientific judgment, may jeopardize the subject or may require intervention (e.g., medical, surgical) to prevent one of the other serious outcomes listed in the definition above). Examples of such events include, but are not limited to, intensive treatment in an emergency room or at home for allergic bronchospasm; blood dyscrasias or convulsions not resulting in hospitalization; or the development of drug dependency or drug abuse.

Version Date: 18MAR2020 Confidential Page 29 of 41

11.1.3 Unexpected Adverse Event

For this study, an AE is considered unexpected when it varies in nature, intensity or frequency from information provided in the current IB, prescribing information or when it is not included in the informed consent document as a potential risk. Unexpected also refers to AEs that are mentioned in the IB as occurring with a class of drugs or are anticipated from the pharmacological properties of the drug, but are not specifically mentioned as occurring with the particular drug under investigation.

11.1.4 Relatedness

AEs will be categorized according to the likelihood that they are related to the study drug(s). Specifically, they will be categorized using the following terms:

Unrelated	Adverse Event is not related to the study drug(s)	
Unlikely	Adverse Event is doubtfully related to the study drug(s)	
Possible	Adverse Event may be related to the study drug(s)	
Probable	Adverse Event is likely related to the study drug(s)	
Definite	Adverse Event is clearly related to the study drug(s)	

11.2 Reporting

11.2.1 Adverse Events

- AEs will be recorded from time of signed informed consent until 30 days after discontinuation of study drug(s) or until a new anti-cancer treatment starts, whichever occurs first.
- AEs will be recorded regardless of whether or not they are considered related to the study drug(s).
- All AEs will be recorded in the subject's medical record and on the appropriate study specific eCRF form within the EDC system.
- AEs considered related to study drug(s) will be followed until resolution to ≤ Grade 1 or baseline, deemed clinically insignificant, and/or until a new anti-cancer treatment starts, whichever occurs first.
- Asymptomatic laboratory abnormalities that do not require treatment will not be collected as adverse events.

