1.4 SGI-110 (Guadecitabine) and its role in platinum re-sensitization

While the FDA-approved demethylating agent decitabine is prone to deamination by cytidine deaminase, Guadecitabine (Astex Pharmaceuticals, Inc.), a dinucleotide analogue of decitabine, is more stable, less toxic, and a promising alternative to restoring silenced tumor suppression genes (TSG) expression in cancer cells by reversal of DNA methylation(21). Guadecitabine is a dinucleotide combining 5-aza-dC and deoxyguanosine that has been shown to be more stable than 5-aza-dC making it an attractive alternative. Guadecitabine is resistant to cytidine deaminase(22). Guadecitabine is currently under investigation in multiple clinical trials including high- risk myelodysplastic syndrome and acute myelogenous leukemia(23). In addition, preclinical data has demonstrated the combination of Guadecitabine with cisplatin in platinum resistant ovarian models re-sensitized ovarian cancer cells to platinum (24). This resensitization was not a result of inhibition of repair of platinum induced DNA as originally thought. DNA damage induced by platinum was increased by Guadecitabine as measured by inductively coupled plasma mass spectrometry analysis. A phase I trial of Guadecitabine and carboplatin in platinum resistant recurrent ovarian cancer was recently completed (25). Guadecitabine was administered once daily subcutaneously on days 1-5 followed by carboplatin IV day 8 of every 28 days cycle. The maximum tolerated dose of the combination was Guadecitabine at 30mg/m² SQ days 1-5 in combination with carboplatin AUC 4 on day 8. The dose limiting toxicities were grade 4 neutropenia and grade 4 thrombocytopenia. Common treatment related adverse events were neutropenia, nausea, fatigue, anemia, injection site

Version Date: 18MAR2020 Confidential Page 9 of 41

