2.2.2 Secondary Endpoints

- Occurrence of all treatment related toxicities as defined by the NCI Common Terminology Criteria for Adverse Events (NCI CTCAE) v5.0
- ORR will include confirmed complete response (CR) + confirmed partial response (PR) and will be determined as per RECIST 1.1 or MDA criteria.
- DCR defined as CR + PR + Stable Disease (SD) per RECIST 1.1 or MDA criteria
- OS as defined as the time from Day 1 of treatment until death from any cause

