6. TOXICITIES AND DOSE DELAYS/DOSE MODIFICATIONS

The NCI Common Terminology Criteria for Adverse Events (CTCAE) v5.0 will be used to grade adverse events. Subjects enrolled in this study will be evaluated clinically and with standard laboratory tests before and at regular intervals during their participation in this study as specified in Study Calendar & Evaluations. Subjects will be evaluated for adverse events (all grades), serious adverse events, and adverse events requiring study drug interruption or discontinuation as specified in Study Calendar & Evaluations.

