6.2 Dose Levels for Dose Reductions

Dose level	Dose of carboplatin	Dose of Guadecitabine
Starting Dose	AUC 4	30mg/m^2
Dose level (-1)	AUC 4	24mg/m ²

Version Date: 18MAR2020 Confidential Page 16 of 41

Dose Modification Guidance Table (applies to Day 1 for all cycles except for Cycle 1)

Neutropen	Neutropenia (absolute neutrophil count [ANC])			
Toxicity	Grade	Stipulations	Suggested Action	
	G3 500 - 999/mm ³ (w/out fever [>38.3°C or 101.0°F])	≤ 14 days of interruption/delay	 hold treatments until ANC >1000/mm³ Prophylaxis with granulocyte colony stimulating factor (G-CSF) starting with next cycle should be considered by treating physician. In these patients GCSF support will be given on Day 6 through an on-body injector (neulasta onpro) no change in Guadecitabine or carboplatin dose 	
	G3 500 - 999/mm ³ (w/out fever)	> 14 days of interruption/delay	 hold treatments until ANC >1000/mm³ Prophylaxis with granulocyte colony stimulating factor (G-CSF) starting with next cycle should be considered by treating physician. In these patients GCSF support will be given on Day 6 through an on-body injector (neulasta onpro) reduce Guadecitabine by one dose level 	
	G3 500 - 999/mm ³ (w/ fever)		 hold treatments until ANC >1000/mm³ Prophylaxis with granulocyte 	
	G4 (w/out fever)	Lasting ≤ 14 days	 Prophylaxis with grandrocyte colony stimulating factor (G-CSF) starting with next cycle should be considered by treating physician. In these patients GCSF support will be given on Day 6 through an on-body injector (neulasta onpro) reduce Guadecitabine by one dose level 	
Any episode	G4 (w/out fever)	G4 lasting > 14 days	discontinue subject from study	

Version Date: 18MAR2020 Confidential Page 17 of 41

Thrombocytopenia			
Toxicity	Grade	Suggested Action	
1	G3 25,000 - 50,000/mm ³	 hold treatments until plt ≥ 50,000/mm³ reduce Guadecitabine by one dose level 	
	$G4 < 25,000/\text{mm}^3$	discontinue subject from study	

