6.3 Protocol Therapy Discontinuation

In addition to discontinuation from therapy related to toxicities as outlined above, a subject will also be discontinued from protocol therapy and followed per protocol under the following circumstances outlined below. The reason for discontinuation of protocol therapy will be documented on the electronic case report form (eCRF)

- Documented disease progression.
- Site investigator determines a change of therapy would be in the best interest of the subject
- Subject requests to discontinue protocol therapy, whether due to unacceptable toxicity or for other reasons
 - In a subject decides to prematurely discontinue protocol therapy ("refuses treatment"), the subject should be asked if he or she may still be contacted for further scheduled study assessments. The outcome of that discussion should be documented in both the medical records and in the eCRF.
- Female subject becomes pregnant
- Protocol therapy is interrupted for ≥ 6 weeks.

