6.4 Protocol Discontinuation

If a subject decides to discontinue from the protocol (and not just from protocol therapy) all efforts should be made to complete and report study assessments as thoroughly as possible. A complete final evaluation at the time of the subject's protocol withdrawal should be made with an explanation of why the subject is withdrawing from the protocol. If the reason for removal of a subject from the study is an adverse event, it will be recorded on the eCRF.

Version Date: 18MAR2020 Confidential Page 18 of 41

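### Section 11.2.1 excludes asymptomatic, untreated laboratory abnormalities from adverse event collection whatever their grade or effect on dosing, so high-grade cytopenias may be missing from the safety data

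*Combined protocol and SAP*

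**What the plan says.** The collection rule in Section 11.2.1 reads: "Asymptomatic laboratory abnormalities that do not require treatment will not be collected as adverse events". It is not qualified by grade or by any effect on dosing.

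Section 11.1.1 defines when a laboratory value is an adverse event at all: "Abnormal laboratory values or diagnostic test results constitute AEs only if they induce clinical signs or symptoms or require treatment or further diagnostic tests". This adds a route, further diagnostic testing, that Section 11.2.1 does not repeat. It also has no exception for grade or dosing.

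Other text leans towards capture:

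- Section 6: "Subjects will be evaluated for adverse events (all grades), serious adverse events, and adverse events requiring study drug interruption or discontinuation".
- Section 6.3 treats the stops in the dose tables as toxicity-related ("In addition to discontinuation from therapy related to toxicities as outlined above") and puts the reason for stopping therapy on the eCRF.
- Section 6.4: "If the reason for removal of a subject from the study is an adverse event, it will be recorded on the eCRF".

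On the expected toxicity of the combination, Section 1.4 says: "The dose limiting toxicities were grade 4 neutropenia and grade 4 thrombocytopenia". The Section 6.2 tables act on neutrophil and platelet counts. For grade 4 platelets, and for afebrile grade 4 neutropenia lasting more than 14 days, the action is "discontinue subject from study".

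The secondary safety endpoint in Section 2.2.2 is "Occurrence of all treatment related toxicities as defined by the NCI Common Terminology Criteria for Adverse Events", version 5.0. Section 12.6.2 tabulates toxicities in the safety population, separately for the two chemosensitivity groups. It does not say whether the source is the adverse event form or the laboratory data.

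**The concern.** The toxicities most expected from this regimen are low blood counts, which are often silent. A rule that drops silent, untreated laboratory findings whatever their grade can drop the events that lead to a hold, a reduction or a stop.

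The rule can only remove events. Haematologic toxicity rates built from adverse event forms may therefore be too low and cannot be too high. Three uses of the data are exposed:

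- the aggregate adverse event updates and the grade 3 or above notification trigger in Section 13.1;
- the adverse event summary sent to the monitoring committee under Section 13.2, whose list of reports contains no summary of laboratory grades;
- the toxicity endpoint, if Section 12.6.2 is built from adverse event forms.

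The two differing rules also allow sites to handle identical events differently. That adds between-site variation to a small data set.

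**Working it through.** The plan states no figure to reproduce here, so the check is mainly textual, with simple arithmetic.

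**1. Which dose-table rows can fall under the exclusion (Section 6.2)**

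| Row | Symptom required? | Treatment named? |
|---|---|---|
| Neutropenia G3, afebrile, delay ≤ 14 days | No | G-CSF to be considered, next cycle |
| Neutropenia G3, afebrile, delay > 14 days | No | G-CSF to be considered, next cycle |
| Neutropenia G3, febrile | Yes (fever) | G-CSF to be considered, next cycle |
| Neutropenia G4, afebrile, ≤ 14 days | No | G-CSF to be considered, next cycle |
| Neutropenia G4, afebrile, > 14 days | No | None |
| Platelets G3 | No | None |
| Platelets G4 | No | None |

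Rows with no symptom condition: 4 + 2 = 6 of 7. Rows that also name no treatment: 3 of 7. In the other three symptom-free rows, G-CSF is optional prophylaxis from the following cycle, and the plan does not say whether that counts as treating the abnormality. These are counts of table rows. They do not show how often the events occur.

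**2. The two rules applied to one case**

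Take an asymptomatic grade 3 platelet count, not transfused, with treatment held and the count repeated until recovery. Under Section 11.1.1 the repeat counts can be read as further diagnostic tests, so the event is an adverse event. Under Section 11.2.1 there is no symptom and no treatment, so it is not collected. The sections give opposite answers.

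For an asymptomatic grade 4 platelet count that ends participation, Section 6.4 records the reason if it is an adverse event, but Section 11.2.1 may mean it is not one.

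Transfusion or filgrastim given under Section 5.3 would bring a case back into collection. The exclusion therefore applies only to untreated cases.

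**3. Effect on the tabulated rate**

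Inputs: planned group sizes of 24 and approximately 10 (Section 12.3), and analysis by group (Section 12.6.2). The safety population is assumed to match these sizes. If k patients have their only grade 3 or above cytopenia unrecorded, the rate falls by k/n:

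| k (assumed) | Chemo-sensitive, n = 24 | Chemo-resistant, n = 10 |
|---|---|---|
| 1 | 1/24 = 4.2 points | 1/10 = 10 points |
| 3 | 3/24 = 12.5 points | 3/10 = 30 points |

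The documents give no cytopenia rate from which to estimate k, so 1 to 3 is illustrative.

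**4. What scheduled laboratory data could recover**

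The Section 7 calendar has blood counts on Days 1 and 5, and footnote 8 lets the Day 1 sample of later cycles be drawn up to 4 days early. The next Day 1 is Day 29. The gap after Day 5 is 29 − 5 = 24 days, or 25 − 5 = 20 days if drawn early, before the ±3-day visit windows. After Cycle 4 the next scheduled count is the safety visit, 30 ± 7 days after the last dose, so 23 to 37 days later. A table from scheduled counts alone would be a lower bound, because mid-cycle nadirs can be missed.

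**The case against.** The best opposing case is that these events stay visible elsewhere and that the literal reading is too strict.

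- **Other channels.** Section 13.1 provides for continuous review and monthly meetings covering significant toxicities. Minutes and monthly summaries go to the monitoring committee. Dose dates are on the eCRF, exposure is described under Section 12.6.4, and the reason for stopping is recorded. Section 11.1.2 gives blood dyscrasias as an example of an important medical event.
- **Reading.** The last bullet of Section 11.2.1 may be only shorthand for Section 11.1.1, under which a held and repeated count could qualify.
- **Endpoint.** Sections 2.2.2 and 12.6.2 speak of toxicities by CTCAE, and Section 12.4 points to a calendar that includes blood counts. Tabulating from laboratory values fits that text at least as well.
- **Size.** It is unknown, and the direction of any bias in the trigger depends on how the Investigator's Brochure and package insert count cytopenias.

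Much of this stands as a limit on the consequences. The loss is possible rather than certain, the endpoint limb is conditional, and no bias in the trigger can be asserted. But none of these channels is a graded adverse event record, and none overrides Section 11.2.1. A serious adverse event must first be an adverse event. The shorthand reading still leaves two sections that differ in words and in result. Laboratory values are not certain to be in the database either: Section 14.2 requires standard-of-care results only in source documents at minimum, with selected items entered in EDC.

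**Conclusion.** The concern holds. Followed as written, Section 11.2.1 keeps asymptomatic, untreated grade 3 or 4 thrombocytopenia, and afebrile grade 4 neutropenia lasting more than 14 days, out of adverse event collection even when Section 6.2 requires action on them. It also conflicts with Section 11.1.1.

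The case is clearest for platelets. It is weaker for the neutropenia rows that mention G-CSF, and it does not apply to febrile or treated cases. The amount of under-recording cannot be determined from the documents; the per-patient steps of 4.2 and 10 points assume safety groups of 24 and 10. Whether the toxicity endpoint is affected depends on the unstated source for Section 12.6.2. This should be corrected: the remedy is cheap and the affected events are the regimen's known dose-limiting toxicities.

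**What to change.** 1. Put one rule in both Section 11.1.1 and Section 11.2.1: any laboratory abnormality of CTCAE v5.0 grade 3 or above, or that leads to a hold, reduction or discontinuation of study drug, is recorded as an adverse event regardless of symptoms or treatment. Trivial low-grade findings can still be left out.
2. State in Section 12.6.2 that haematologic and chemistry toxicity is also tabulated as worst CTCAE v5.0 grade per patient, from all available scheduled and unscheduled CBC and CMP results, separately by chemosensitivity group. Add a note that the table is a lower bound because of the gaps between scheduled counts.
3. Include these laboratory grades in the summaries sent to the monitoring committee under Section 13.2.

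The cost is wording in two protocol sections and one analysis section, an addition to the committee summaries, one derived table, and entry of CBC and CMP values (including unscheduled ones) in EDC where not already captured. That last item may be the largest and is not sized here. The reported toxicity rate may be higher. No test or visit is added and no dose rule changes.
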